A Norwegian study included 24 individuals with mixed diagnoses and extensive use of hospital admission (Støvind, Hanneborg, Ruud, 2012). Eight of the individuals had schizophrenia, and the remaining participants had affective disorder (n=7), anxiety disorder (n=4), personality disorder (n=3), substance abuse (n=1) or lacked a diagnosis (n=1). The participants could themselves decide when they wanted to be admitted to hospital, and stay for durations of up to five days. After an admission period, they had to be treated in an ambulatory setting for at least 14 days before they again had the opportunity to choose another five-day admission. The total number of participants was small and the study made no estimates of significance, but the number of involuntary admissions was halved, and participants reported feeling more satisfied with their care when brief admissions were included. For participants with schizophrenia, the number days of hospital admission did not change with the intervention possibly due to the course of acute psychosis. However, for the remaining sixteen participants, hospital admission decreased from 37% of the days during the six months preceding the intervention, to 13% of the days during the six months of intervention. The frequency of admissions increased, but each admission lasted on average only two to three days.

Description of the project

Sites:

Psykiatri Skåne provides inhabitants in Region Skåne with psychiatric healthcare. Region Skåne has about 1,3 million inhabitants and is served by four geographically organized psychiatric divisions (Helsingborg, Kristianstad, Lund and Malmö) and two that are organized by content (Child and Adolescent Psychiatry and Forensic Psychiatry). The geographically based divisions are served by four inpatient settings (Helsingborg, Kristianstad, Lund and Malmö) and several ambulatory units. About 3000 people are currently employed at Psykiatri Skåne. Researchers conducting the study are based in Lund ([name], [name], [name] and [name]) where the administrative center of Region Skåne also is located, and in Groeningen, the Netherlands ([name]). The pilot phase of the study will take place in Lund and Malmö.

Definitions

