The design for this project will be a Randomized Control Trial (RCT), combined with Time-series (TS; Borckardt et al, 2008). Participants will be randomized at an individual level to either BA + Treatment as Usual (TAU) or TAU. Block randomization, using tables with random numbers with blocks of four, will be used in order to minimize the confounding effect of changes in general care over time. Randomization will be stratified according to site (i.e. Lund, Malmö, Kristianstad, Helsingborg). Random number tables will be generated in SPSS. The data will be handled with Intention to treat (ITT) analysis, so that once participants are randomized, their data will be included in all analyses regardless of whether they drop-out of the study prior to its termination.

Every participant receives a consecutive research number indicating to which site they belong (Lund – L01-..., Malmö – M01 - ...; Kristianstad – K01-..., Helsingborg – H01-...). The researcher who is methodologically responsible prepares the randomization lists in four series

(one per site). The randomization numbers are named according to strata (Lund – LR01-..., Malmö – MR01 - ...; Kristianstad – KR01-..., Helsingborg – HR01-...). From the lists, a research nurse prepares four series of consecutively numbered, sealed, opaque envelopes, each containing information on which group the participant is randomized to. After inclusion in the study, the research participant is given the envelope to open. After reading, PI handles a letter containing information on which upcoming procedures for the group to which the participant has been randomized. The randomization enveloped is handled back to PI and stored in a locker, together with the master key.

In the master key, PI register the name of the participant in combination with the research code and the randomization code. Data from forms are collected online, encoded by the research number, and stored on Lund University server. These assessments will be blinded to researchers analyzing the data. Videos and audio-recordings will be stored on USB in a locker separate from the master key. Recordings will only be reviewed on computers not connected to Internet.

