A defining feature of the BA is that the participant decides for themselves regarding whether and when to initiate a brief hospital admission, at most three times per month, and for a maximum of three consecutive days. BAs can be initiated between 8AM and 8PM every day during the week. The procedure for the BA is defined in the BASP. If the needs of the client exceed the level of service offered during BA, GA should be considered.

The intervention will last for 12 months and the participant will evaluate the intervention at the end of each BA and the contract after 6 and 12 months according to the procedure as described in BASFM (Bilaga 2b; Liljedahl, Helleman, Daukantaite & Westling, 2017). Participants randomized to the BA condition have access to the same security procedures as they do when receiving Treatment as Usual (TAU).

No risks to the well-being of the participant are expected, exceeding those found with TAU. Normal security routines are therefore sufficient. Data collection will start in September 2015 for the pilot phase of the study, and evaluated at the end of January 2015.

How is the choice of methods related to the Research Objectives?

1. Can BA replace GA for individuals with self-harm and acute risk for suicide?
 - Outcome is data from medical records.
2. Can BA increase the individual's level of functioning in activities of daily life?
 - Outcome is data from WHODAS 2.0. (World Health Organization, 2014).
3. Can BA increase the individual's ability to cope effectively with life stress?
 - Outcome is data from Brief COPE (Carver, 1997) Swedish version of the Brief COPE (Muhonen & Torkelson, 2005) and DERS (Gratz & Roemer, 2004); Swedish version of the DERS (Friberg, 2006).
4. Can BA reduce the individual's global psychiatric symptoms?
 - Outcome is data from estimation according to CGI-S (Guy, 1976).
5. Can BA reduce the frequency of all self-harming behaviours including suicide attempts?

- Outcome is data from questionnaire 5S-HM (Liljedahl & Westling, 2014) and ISAS (Klonsky & Glenn, 2009; Glenn & Klonsky, 2011; Lindholm, Bjärehed & Lundh, 2011).

6. Can BA affect the severity of self-harming behaviours including suicide attempts?
 - Outcome is data from questionnaire 5S-HM (Liljedahl & Westling, 2014).
7. Can BA serve as a feasible management option in the care of individuals with self-harm who may also be at risk for suicide?

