 - Outcome is data from IES and the CES (Liljedahl, Helleman, Daukantaite & Westling, 2017) completed by the participants and clinicians administering BA after pilot testing, 6 and 12 months
8. Can the *Five Self-Harm Behaviour Groupings Measure* (5S-HM: Liljedahl & Westling, 2014) reliably and validly measure behaviors ranging from indirect to direct self-harm and attempted suicide, with varying degree of frequency and severity?
 - Outcome is data from questionnaire 5S-HM (Liljedahl & Westling, 2014), ISAS (Klonsky & Glenn, 2009; Glenn & Klonsky, 2011); Swedish version of the ISAS (Lindholm, Bjärehed & Lundh, 2011) and DERS (Gratz & Roemer, 2004); Swedish version of the DERS (Friberg, 2006).

Required sample size and a priori power analyses

G*Power, 3. 1. 7 (Faul, Erdfelder, Lang, & Buchner, 2007) was used to calculate a priori power for analyzing main effects and interaction for an A X B mixed design where A is a between-subject factor with two levels (experimental and control groups) and B is a within-subjects factor with three levels (three repeated assessments). The main statistical analyses will be either mixed (within-between) Analysis of Variance (ANOVA) or Analysis of Covariance (ANCOVA), controlling for baseline. Simpler univariate analyses will be calculated, but the power analyses summarized here are for the ANOVA model.

Assuming that three effects (i.e., between levels of the factor A, within levels of the factor B and within-between interaction A X B), are of medium size ($f = 0.25$; see Cohen, 1988), a significance level is of $\alpha = .05$, and the power values of the F tests are .85, a total of $N = 98$ per treatment site must be recruited ($n=196$ including both Stockholm and Lund, whose data will be grouped and analyzed separately).

Attrition in this population based on previous studies has been estimated to be approximately 25% (Stoffers, Völlm, Rucker, Timmer, Huband & Lieb, 2012; Nadort, Arntz, Smit, Giesen-Bloo, Eikelenboom, Spirnhoven, van Asselt, Wensing, & van Dyck., 2009). In order to attain the required sample size for these power estimates, including expected attrition, a total of $N= 124$ participants is required, with $n=62$ participants in each group (treatment and control).

Significance:

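### The target of 124 does not retain the required 98 at the plan's own 25% attrition (it leaves 93), and the unit to which the 98 applies is unclear

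*Combined protocol and SAP*

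**What the plan says.** All the sample-size figures are in the section Required sample size and a priori power analyses. The calculation is for a mixed ANOVA with two groups and three repeated assessments, f = 0.25 for the between, within and interaction effects, alpha .05 and power .85. The result is 98 per treatment site and 196 in total, "including both Stockholm and Lund, whose data will be grouped and analyzed separately".

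The next paragraph turns to losses: "Attrition in this population based on previous studies has been estimated to be approximately 25" per cent. It concludes: "In order to attain the required sample size for these power estimates, including expected attrition, a total of $N= 124$ participants is required", with 62 in each group.

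Elsewhere the trial is described as a Skåne trial. Under Sites: "The geographically based divisions are served by four inpatient settings (Helsingborg, Kristianstad, Lund and Malmö". Under Study design: "Randomization will be stratified according to site (i.e. Lund, Malmö, Kristianstad, Helsingborg". Stockholm is not named as a site in either place.

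Two further statements bear on how much attrition matters. Under Study design, once participants are randomised, "their data will be included in all analyses regardless of whether they drop-out of the study prior to its termination". For the primary research question, the section linking methods to research objectives says: "Outcome is data from medical records".

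**The concern.** The attrition sentence makes a claim that can be checked: 124 is enough to deliver the required number after the stated loss. An allowance for a proportional loss d divides the required number by (1 − d). The stated 124 looks like multiplication by (1 + d), which always gives too few.

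The site wording raises a second question. A requirement of 98 at each of two separately analysed sites means 196 before any attrition, and 124 is below that. A requirement of 98 for Skåne as a whole fits 124 much better, but the text does not say so.

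At stake is whether the stated power holds at the stated attrition, and whether a reader can tell what population the target covers.

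**Working it through.** **Inputs from the sample-size section:** f = 0.25; alpha = .05; power = .85; k = 2 groups; m = 3 assessments; required N = 98; attrition 25%; target 124 (62 per group). **Not stated:** the correlation ρ among repeated assessments. I assume 0.5 and show 0.3 and 0.7 as a range.

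**1. Reproducing 98.** For the between-group effect the noncentrality is λ = f²·N·m / (1 + (m − 1)ρ), with 1 and N − 2 degrees of freedom. At N = 98 and ρ = 0.5, λ = 0.0625 × 98 × 3 / 2 = 9.19, and power is 0.851. This is the smallest even N that reaches .85, so the plan's 98 is reproduced. At ρ = 0.5 the within and interaction effects need only 32, so the between-group effect sets the requirement.

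**2. Reproducing 124.** Half of 98 is 49 per group.
- Multiplying: 49 × 1.25 = 61.25, rounded up to 62 per group, total 124. This matches the plan.
- Dividing: 49 / 0.75 = 65.33, rounded up to 66 per group, total 132.

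The plan does not show its inflation step. Multiplication by 1.25 is an inference from the match.

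**3. What 124 delivers.**
- At 25% attrition: 124 × 0.75 = 93, which is 5 short of 98.
- Attrition at which 98 remain: 1 − 98/124 = 0.210.
- Check on 132: 132 × 0.75 = 99.

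None of this depends on ρ.

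**4. Effect on power.** The interaction uses λ = f²·N·m / (1 − ρ), with 2 and 2(N − 2) degrees of freedom, assuming sphericity.

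| | ρ = 0.3 | ρ = 0.5 | ρ = 0.7 |
|---|---|---|---|
| Between-group, N = 98 | 0.918 | 0.851 | 0.782 |
| Between-group, N = 93 | 0.904 | 0.832 | 0.760 |
| Between-group, N = 124 | 0.966 | 0.923 | 0.870 |
| Interaction, N = 93 | 0.996 | 0.9998 | >0.999 |
| Even N for .85, between-group | 80 | 98 | 118 |

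The slip costs about two points of between-group power or less at ρ = 0.3 and 0.5, and 0.782 − 0.760 = 0.022 at 0.7. The unstated correlation matters more: across the same range it moves the required N from 80 to 118.

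**5. Site wording.** If 98 really is needed at each of two sites, the total is 196 before attrition and 196 / 0.75 = 261.3 after it, or 264 as two sets of 132. The single target of 124 cannot be that number. It is consistent with one inflated set of 98. The four Skåne strata fit neither a two-site count nor a per-site requirement of 98.

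**The case against.** The strongest reply is that little follows from the slip. At the correlation that reproduces the plan's own 98, power falls from 0.851 to 0.832, and the plan's attrition figure is itself approximate. That stands, and it is why no larger sample is asked for.

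Second, the between-group main effect may not be the treatment test that matters. It averages in the baseline assessment, whereas a benefit arising after baseline shows in the group-by-time interaction, which remains very well powered. Even without sphericity, at the worst-case correction (epsilon 0.5), ρ = 0.3 and N = 93, interaction power is 0.937. The plan also allows ANCOVA adjusted for baseline. As an illustration, a 0.5 SD difference at both follow-ups, analysed as their mean adjusted for baseline, has power 0.890, 0.921 and 0.978 at N = 93 for ρ = 0.3, 0.5 and 0.7. This also stands as to weight, although the plan does not choose between the two models and its calculation is for the ANOVA.

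Third, the primary outcome comes from records and drop-outs are kept in the analysis, so 93 is the pessimistic case there. If all 124 contribute records, between-group power is 0.923 at ρ = 0.5. But WHODAS 2.0, Brief COPE, DERS, 5S-HM and ISAS need participants to complete forms, and the plan itself applies 25% to these power estimates. The sentence remains wrong on its own terms.

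Finally, Lund can be read as shorthand for the Skåne part of a wider project, since the Sites section places the regional administration there. That is plausible, but the documents do not say it.

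**Conclusion.** The concern holds. At the stated 25% attrition, 124 leaves 93 and does not attain 98; it does so only up to 21.0%. This rests on the plan's figures alone.

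The practical effect is minor. Between-group power falls from 0.851 to 0.832 if ρ = 0.5. At 0.3 it stays above .85 even with 93 (0.904); at 0.7 it is below .85 already with 98 (0.782). Interaction power is at least 0.996 at 93 across that range under sphericity. For the records-based primary outcome the loss may be smaller than 25%.

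The Stockholm and Lund wording is an unresolved ambiguity, not a proven error: the documents do not show whether a parallel Stockholm study exists. The statement should be corrected because it is the trial's sample-size justification, not because the trial is materially underpowered.

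**What to change.** Keep 124 and restate what it provides:

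- It retains 98 only up to 21% attrition. At 25% it leaves 93, with about 83% power for the between-group effect if the correlation is 0.5, and interaction power above 0.99 under sphericity.
- State the repeated-measures correlation actually entered in the power program. If it was not 0.5, recompute the power figures with it.
- Say whether the 25% applies to the records-based primary outcome or only to outcomes that need a visit or questionnaire.
- Reconcile the per-site 98 and the total of 196 with the four Skåne strata and the target of 124. If Stockholm is not part of this trial, give 98 as the total across the Skåne sites and delete the parenthesis. If a parallel Stockholm study exists, say so, and say that 124 is the Skåne target alone.

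The cost is a few sentences of text. No additional participants and no change of design or analysis are needed.
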